4.3.1.2. Exploratory Efficacy Endpoints (Bladder Diary)

4.3.2. Patient Reported Questionnaire Endpoints

4.3.2.1. International Prostate Symptom Score

The International Prostate Symptom Score (IPSS) is based on the responses to 7 questions concerning urinary symptoms and 1 question concerning quality of life. Each question concerning urinary symptoms allows the subject to choose 1 out of 6 answers indicating increasing severity of the particular symptom. The responses are assigned points from 0 to 5. The total score can therefore range from 0 to 35 (asymptomatic to very symptomatic).

The questions refer to the following urinary symptoms:

[figure not shown]
Questions	Symptom
1	Incomplete emptying
2	Frequency
3	Intermittency
4	Urgency
5	Weak Stream
6	Straining
7	Nocturia

[figure not shown]
Question 8 refers to the subject's perceived quality of life (QoL). The answers to the single question to assess the quality of life this question range from 0: "delighted" to 6: "terrible".

[figure not shown]
The IPSS questions reference storage symptoms (frequency, urgency and nocturia scores) and voiding symptoms (incomplete empty, intermittency, weak stream and straining) [1]. The following parameters will be derived:

CFB in IPSS storage score to Week 52 (secondary efficacy)

The IPSS storage score will be derived as the sum of the IPSS storage questions (sum of frequency, urgency and nocturia scores) for each visit. If any of these questions are not answered, the IPSS storage score will not be calculated.

Function Domain	Questions	Direction of Domain Scores

4.3.3. Study Day and Duration

Study day is relative to the start date of the double-blind treatment on the parent study URO-901-3005. This is used to describe the relative time of an event or assessment that happened during the study. The first day of the study is defined as the day a patient first receives either vibegron or placebo in the double-blind treatment period. This is expected to be the same day as the randomization as Day 1. There is no study Day 0 defined in the study.

- For event or assessment that occurred on or after the first dose of double-blind treatment date:

$$\text{Study day} = \text{Date of event or examination} - \text{date of first study treatment} + 1$$
- For event or assessment that occurred prior to the first dose of double-blind treatment date:

$$\text{Study day} = \text{Date of event or examination} - \text{date of first study treatment}$$

Treatment day will be defined in the same manner relative to the date of first dose of vibegron.

Similarly, a duration between any two dates (such as AE duration) expressed in days will be calculated using the following conventions:

- $\text{Duration} = \text{Later date} - \text{earlier date} + 1$

4.3.4. Baseline and Change from Baseline

In general, the last recorded value on or prior to the date of randomization in the parent study URO-901-3005 will serve as the baseline measurement for efficacy endpoints while the last recorded value prior to first double-blind dose of study treatment will serve as the baseline measurement for safety endpoints. The mean of multiple values will be used as baseline for the following situations:

- If multiple measurements are scheduled on the same baseline day (i.e., blood pressure)
- If multiple measurements are collected on the same baseline day without the time or “repeat” status to differentiate the records

For efficacy endpoints derived from the Bladder Diary, the baseline will be the average value over the diary days in the baseline analysis visit window on study URO-901-3005.

Change from baseline will be calculated as the post-baseline value minus the baseline value. Percentage change from baseline will be calculated as the change from baseline divided by the baseline value, multiplied by 100. If either the baseline or post-baseline value is missing, then change from baseline and percentage change from baseline will be set to missing.

5. Demographics, Other Baseline Characteristics, Procedures And Medication

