1.1. Study Objectives and Endpoints

Assessments in Study URO-901-3006 are referenced to the initial Baseline (Visit 3) from Study URO-901-3005. Change from baseline (CFB) study endpoints for safety parameters for study URO-901-3006 are relative to the most recent assessment prior to starting vibegron. CFB study endpoints for efficacy in Study URO-901-3006 are relative to Study URO-901-3005 baseline. At the Week 52 visit, CFB comprises 52 weeks of vibegron exposure for subjects randomized to vibegron in Study URO-901-3005 and 28 weeks of vibegron exposure for subjects randomized to placebo.

With respect to study endpoints, “per day” refers to a “Diary Day”, which is defined as the time between when the subject gets up for the day each morning and the time the subject gets up for the day the next morning as recorded in the subject bladder diary (approximately a 24-hour period).

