3.1.2. Safety Analysis Set Extension

The Safety Analysis Set Extension (SAF-Ext) will serve as the primary population for the analysis of safety data in this trial.

The SAF-Ext consists of all randomized subjects in Study URO-901-3005 who

- a) have completed the 24-week treatment period in the Study URO-901-3005, and
- b) enrolled into the extension Study URO-901-3006 and received at least one dose of vibegron in this study.

Safety endpoints will be descriptively summarized for the entire Safety Analysis Set Extension. No imputation will be performed for missing safety data. Baseline will be established as the last observation prior to the first dose of vibegron. All safety data collected on or after the first exposure to vibegron within the combined experience of the patient on URO-901-3005 and

URO-901-3006 will be included in the safety analysis for URO-901-3006, and all analyses by visit will index visits from the first dose of vibegron on either study; subjects who received placebo in study URO-901-3005 will only contribute safety data up to Week 28.

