2. For non-early withdrawal records, if a nominal visit number for a scheduled visit was assigned, then it will be used to summarize the record after checking to make sure that visit numbers match with therapy phases:

- Check that all records entered as a pre-treatment visit for study URO-901-3005 occur on or before the day of the first dose of double-blind treatment (i.e. day ≤1). Any record with day > 1 should be re-slotted to an on-treatment visit using the relative day window below.
- Check that all records slotted to an on-treatment visit for study URO-901-3005 and all records for study URO-901-3006 are on or after the day of the first dose of double-blind treatment. If they are not, the visit should be moved to pre-treatment.

3. Any early withdrawal record (regardless of the visit number assigned), any unscheduled visit record at any time, any repeat visit record, or any record for which the visit number was missing or the visit number was not for a scheduled visit, should be slotted or re-slotted to a visit using the window below.

Table 4: Analysis Visit Window Slotting

Analysis window label	URO-901-3005 Randomized Arm					
	Vibegron			Placebo		
	Nominal visit	Nominal day	Visit Window	Nominal visit	Nominal day	Visit Window
Baseline	Visit 3	1	NA ^a	Visit 3	1	[1,182 ^b]
Week 1	Visit 4	8	[2, 11]	NA	NA	NA
Week 2	Visit 5	15	[12, 22]	NA	NA	NA
Week 4	Visit 6	29	[23, 42]	Visit 12	197	[183 ^c ,224]
Week 8	Visit 7	57	[43, 70]	NA	NA	NA
Week 12	Visit 8	85	[71, 98]	Visit 13	253	[225,308]
Week 16	Visit 9	113	[99, 126]	NA	NA	NA
Week 20	Visit 10	141	[127, 154]	NA	NA	NA
Week 24	Visit 11	169	[155, 182 ^a]	NA	NA	NA
Week 28	Visit 12	197	[183 ^b , 224]	Visit 14	365	> Day 309
Week 36	Visit 13	253	[225, 308]	NA	NA	NA
Week 52	Visit 14	365	> Day 309	NA	NA	NA

a Must have occurred prior to the first dose administered in study URO-901-3005.

b Must have occurred prior to the date of first dose administered in study URO-901-3006.

c Must have occurred on or after the date of first dose administered in study URO-901-3006.

Note: The cut-off days to define the window for slotting through Week 20 are aligned with study URO-901-3005.

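### For men who took placebo in the parent study, the SAP gives two safety baselines 168 days apart: Day 1 in 4.3.4, and the last value before vibegron in 1.1 and 3.1.2

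*SAP*

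**What the plan says.** Three places in the SAP state the safety baseline.

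- Section 4.3.4, the section that defines baseline: "the last recorded value prior to first double-blind dose of study treatment will serve as the baseline measurement for safety endpoints". Section 4.3.3 defines Day 1 as "the day a patient first receives either vibegron or placebo in the double-blind treatment period", so for a placebo-arm man the first double-blind dose is placebo.
- Section 1.1: change from baseline in "safety parameters for study URO-901-3006 are relative to the most recent assessment prior to starting vibegron". The next sentence of 1.1 keeps the parent-study baseline for efficacy.
- Section 3.1.2: "Baseline will be established as the last observation prior to the first dose of vibegron". It adds that "all analyses by visit will index visits from the first dose of vibegron on either study" and that "subjects who received placebo in study URO-901-3005 will only contribute safety data up to Week 28".

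Table 4 (Section 4.2.4.2) gives the placebo arm a baseline window of Days 1 to 182, with the footnote "Must have occurred prior to the date of first dose administered in study URO-901-3006", and no Week 24 row. It labels the same baseline row Visit 3, nominal Day 1.

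The protocol (synopsis, Section 3 and Section 9.3.2) uses the parent-study baseline throughout. SAP Section 9 lists four changes from the protocol: IPSS Storage wording, exploratory timepoints, COVID-19 and physical examination. The safety baseline is not among them.

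**The concern.** Men randomized to vibegron have the same baseline under either rule. For ex-placebo men the rules select different records, and two programmers who each follow the SAP could produce different tables.

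Long-term safety is the primary objective. Four of its five endpoints in SAP 1.1.1 have change-from-baseline summaries: laboratory values, vital signs, PVR and Total IPSS. Visits are labelled by weeks on vibegron. Under 4.3.4, a change reported for the 28-week group at a vibegron-week label would include everything that happened during 24 weeks on placebo. Adverse events are handled the other way: an event that starts on placebo before the first vibegron dose counts as medical history, not as treatment-emergent (SAP Table 2).

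**Working it through.** **Study days.** With no Day 0 (SAP 4.3.3), study day = 7 × week + 1. Weeks 24, 28, 36 and 52 give Days 169, 197, 253 and 365, which match the protocol's Schedule of Assessments. The two baselines for ex-placebo men are 169 − 1 = 168 days (24 weeks) apart.

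**Placebo share of the change interval under 4.3.4.** Share = 168 / (visit day − 1).

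- Week 4 label (Visit 12, Day 197): 168/196 = 86%. Visit 12 has vital signs and PVR, but no laboratory tests or IPSS.
- Week 12 label (Visit 13, Day 253): 168/252 = 67%.
- Week 28 label (Visit 14, Day 365): 168/364 = 46%.

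Under 1.1 and 3.1.2 the intervals are 28, 84 and 196 days, and the placebo share is 0%.

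**What the choice can do.** With assumed values, a shift of +5 on placebo and 0 on vibegron is reported as +5 under 4.3.4 and 0 under 1.1 and 3.1.2. A shift of −5 on placebo and +5 on vibegron is reported as 0 and +5.

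**Effect on the columns.** Let d be the mean change on placebo. The 28-week column moves by d. The Overall column moves by s × d, where s is the ex-placebo share of the men contributing.

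- SAP 1.2.4 expects 100 one-year completers after about 33% dropout. If that dropout applies to the extension, 100/0.67 = 149 vibegron-arm men, leaving 300 − 149 = 151 ex-placebo (50%). This split is inferred, so I take 40% to 60% (120 to 180 of 300) as the range.
- Vibegron-arm men have no dropout at the Week 4 and 12 labels, because everyone in the set must "have completed the 24-week treatment period in the Study URO-901-3005".
- High end, Week 4 label, 60% ex-placebo, even dropout over 28 weeks: 180 × (1 − 0.33 × 4/28) = 171.5; 171.5/(171.5 + 120) = 0.59.
- Low end, Week 28 label, 40% ex-placebo, full dropout in that arm and none in the other: 120 × 0.67 = 80.4; 80.4/(80.4 + 180) = 0.31.
- Sensitivity at the 50% split, Week 28: 151 × 0.67 = 101; 101/(101 + 149) = 0.40. Step 3 of 4.2.4.2 slots early-withdrawal records by window, so a man leaving after Day 309 still counts at Week 28. If those visits take place, 151 × (1 − 0.33 × 141/196) = 115, where 141 = 310 − 169 and 196 = 365 − 169; 115/(115 + 149) = 0.44.

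So s is roughly 0.3 to 0.6 where both groups contribute, and the documents support nothing finer. For scheduled laboratory tests at the Week 28 label only ex-placebo men contribute, since Visit 12 has none, and the Overall column moves by the whole of d.

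**Table 4.** The window and its footnote fit the pre-vibegron rule. The Day 1 anchor does not: where a window holds several records, step 4 of 4.2.4.2 takes the one closest to the nominal day, which here is the Day 1 record.

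**The case against.** The best defence is that the intent is clear. Section 4.3.4 opens with a general qualifier, so it can be read as a default. Sections 1.1 and 3.1.2 are specific to this study, visits are indexed from first vibegron, Table 4 extends the placebo baseline window to the first extension dose, and 7.8 words baseline separately for the 28-week group. This stands as evidence of intent, since most of the SAP favours the pre-vibegron baseline. It does not settle the rule: 4.3.4 states no exception for ex-placebo men, and the Table 4 anchor points the other way. Protocol 9.3.2 does not settle it either. It leaves the further inclusion of parent-study data to the SAP, but fixes the baseline itself.

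The defence is also right that nothing here is tested and that no material change on placebo has been shown.

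A reader might infer more than the documents support:

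- That 4.3.4 is the undeclared departure from the protocol. It agrees with the protocol; the unlisted change is the rule in 1.1 and 3.1.2.
- That the 86%, 67% and 46% measure bias. They are shares of calendar time.
- That the Overall shift can be given to two decimals. It depends on the group split, dropout and withdrawal-visit slotting, and for laboratory values at Week 12 on a parent-study laboratory schedule that these documents do not give.
- That Baseline and Pre-existing Hypertension status must change. Section 5.2 does not say which baseline it uses, so they may.

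**Conclusion.** The contradiction is real, and the documents do not resolve it. It concerns ex-placebo men only.

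- **Depends on the choice (28-week group, and Overall where these men contribute):** change from baseline in vital signs, PVR, laboratory values and Total IPSS; laboratory shift tables; consecutive-visit counts and maximum and end-of-treatment changes in vital signs; observed values and PVR categories in the baseline row.
- **Does not depend on it:** post-baseline observed values, treatment-emergent status, the eDISH plots, the 52-week column and Week 52 outputs. Section 3.1.2 admits safety data only from first vibegron and takes ex-placebo men only to Week 28.

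If 4.3.4 is followed, the 28-week column moves by the mean change on placebo, and the Overall column by roughly 0.3 to 0.6 of it where both groups contribute. That range assumes 40% to 60% ex-placebo men and the plan's 33% dropout. The harm would be mislabelled change in descriptive tables for the primary objective. Final analysis follows lock of both studies and unblinding of the parent study (SAP 2.2), so a choice left until then would be post hoc.

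**What to change.** 1. In 4.3.4 write: *For safety endpoints, baseline is the last value before the first dose of vibegron (before parent-study Day 1 dosing for the vibegron arm; before the first 3006 dose for the placebo arm).*
2. In Table 4, anchor the placebo-arm baseline at Visit 11, Day 169, and take the latest record before the first 3006 dose.
3. List the departure from the protocol baseline in Section 9.
4. In 5.2, state which baseline defines Baseline Hypertension and baseline Total IPSS.

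If the sponsor prefers the protocol baseline, change 1.1, 3.1.2 and Table 4 instead, and label the 28-week change columns as including 24 weeks on placebo.

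The cost is a few lines of text and one baseline-flag rule. No new data are needed, because the Week 24 assessments already serve as the extension's entry assessments (Protocol 8.1). The downside of the pre-vibegron rule is that the safety baseline then differs from the efficacy baseline and from the parent-study baseline in the hypertension definition of Protocol 8.4.6. Table footnotes saying so would help but are optional.

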5.1. Subject Disposition and Withdrawals

Subject disposition will be summarized by treatment group and overall for the consented and treated subjects. The summary table will present the frequency and percentage of subjects in each of the analysis sets, treatment on URO-901-3006, and those who discontinued the study prematurely along with the primary reasons for discontinuation.

For the summary of the treated subjects, the following additional categories will be presented as well; discontinued treatment with study drug (and reason), completed study, and withdrawn from study (and reason).

The frequency and percentage of subjects with at least one major Protocol Deviation (PD), major PD by classification and reasons/category for PD will be summarized by planned overall treatment duration and overall for the FAS-Ext. Inclusion in each of the analysis sets (SAF-Ext, FAS-Ext, FAS-Ext-I, PPS-Ext, PPS-Ext-I), and any reasons for exclusion will be summarized by planned overall treatment duration for the Treated Set.

Eligibility criteria, screening failures (including date and primary reason for failure), and informed consent (protocol version, informed consent version date and date signed) will be listed for all patients screened.

A summary of treated subjects by country and investigator will be provided. Randomization details will also be listed, including the date of randomization, randomization number and randomization strata.

5.2. Demographic and Baseline Characteristics

All demographic and baseline characteristic data will be summarized by planned overall treatment duration and overall using descriptive statistics for all subjects for each of the following analysis sets: SAF-Ext, FAS-Ext, FAS-Ext-I, PPS-Ext and PPS-Ext-I.

The summary table will include Ethnicity and Race, Region (US and non-US), Prior Anticholinergic Use (Yes/No), Prior Beta-3 agonist Use (Yes/No), Diabetes Mellitus (Yes/No), Baseline Hypertension (Yes/No), Pre-existing Hypertension (Yes/No), Age category 1 (<55, ≥55 to <65, ≥65 to <75, ≥75 years), Age category 2 (<65, ≥65 years), Age category 3 (<65, ≥65 to <85 years, ≥85 years), baseline average micturition episodes per day (≤ 12 vs > 12), Alpha blocker use with or without 5-ARI (with vs without), Urinary Incontinence (yes or no), total IPSS score, alpha blocker (tamsulosin, doxazosin, alfuzosin, other), and 5-ARI (finasteride, dutasteride, other).

Prior Anticholinergic Use and Prior Beta-3 agonist Use will be calculated from all prior medications documented on the Prior and Concomitant Medications electronic case report form (eCRF).

Baseline Hypertension will be defined as baseline systolic blood pressure (SBP) ≥ 140 mmHg or baseline diastolic blood pressure (DBP) ≥ 90 mmHg, regardless of medical history.

Pre-existing hypertension will be defined as having a medical history of hypertension or Baseline hypertension (baseline SBP ≥ 140 mmHg or baseline DBP ≥ 90 mmHg). The following list of preferred terms will be used to search for medical history of hypertension:

- Accelerated hypertension
- Diastolic hypertension
- Essential hypertension
- Hypertension
- Hypertensive crisis
- Hypertensive emergency
- Hypertensive heart disease
- Malignant hypertension
- Malignant hypertensive heart disease
- Secondary hypertension
- Supine hypertension
- Systolic hypertension

Age (years), height (cm), weight (kg), BMI captured at Screening on study URO-901-3005, and baseline IPSS total score will be summarized as a continuous variable.

Unless otherwise stated, percentages will be calculated out of the number of patients in the given analysis set.

All demographic data will be listed.

5.3. Other Baseline Characteristics

The data from the 3-day bladder diary during run-in period on study URO-901-3005 (reviewed at Visit 3 Baseline visit) prior to first dose of double-blind medication will be used as baseline for each subject. This includes average daily number of micturition episodes, average daily number of urgency episodes, average number of nocturia episodes per night, average daily number of urge urinary incontinence episodes, and average volume voided per micturition. In addition, the baseline IPSS storage score will be presented. These will be summarized by treatment group and overall using descriptive statistics for continuous data for all subjects in FAS-Ext, FAS-Ext-I, PPS-Ext and PPS-Ext-I analysis sets.

5.4. Medical History and Concomitant Disease

Descriptions of medical history findings will be coded using Medical Dictionary for Regulatory Activities (MedDRA) version 23.0 or higher.

Medical history will include all events entered on the medical history form in URO-901-3005 as well as any AEs with the end date prior to the first date of active treatment on either URO-901-3005 or URO-901-3006.

A disease or illness reported as medical history without a start date will be included in medical history without a date assigned. Medical history will be sorted by descending overall frequency, by system organ class (SOC) and preferred term (PT) in the summary table. Medical history data listings will be sorted by treatment, subject number, start date, SOC and PT. The SAF-Ext will be the analysis set for medical history data.

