4.2.4. Assessment Windows

4.2.4.1. Study Reporting Periods

Based on study design and variables under consideration, study time periods are defined as below.

Table 2: Definition of Study Reporting Periods

Analysis description	Analyzing Study Period	Start Date	End Date
General	Pre Treatment (Day -49 – Day 1/Week 24)	Date of informed consent	Prior to the date of first dose of vibegron on either study URO-901-3005 or URO-901-3006
	Treatment (Day 1/Week 24 – Week 52)	Date of first dose of vibegron on either study URO-901-3005 or URO-901-3006	Date of last dose of vibegron on URO-901-3006 + 5 or EOS, whichever is earlier
Adverse events	Prior (Summarized as Medical History)	Start date \geq date of informed consent on URO-901-3005 and $<$ date of first dose of vibegron in either study.	No restriction
	Treatment Emergent (TEAE)	Start date (AE begins or worsens in severity) \geq date of first dose of vibegron* and \leq date of last dose of vibegron + 5 days or EOS visit, whichever is earlier.	No restriction

Analysis description	Analyzing Study Period	Start Date	End Date
Prior or Concomitant Medication/ Procedure	Prior medication/ procedure	Start date < date of first vibegron dose	End date < date of first vibegron dose OR medication not marked as ‘ongoing’ on study URO-901-3005 and subject received placebo on study URO-901-3005
	Concomitant medication/ procedure	Start date \geq date of first dose of vibegron and \leq date of last vibegron dose + 5 days or EOS visit, whichever is earlier.	
		Start date < date of first vibegron dose, but ongoing during vibegron treatment period	End date \geq date of first vibegron dose OR medication marked as ‘ongoing’ on study URO-901-3005.

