7.3. Adverse Events

AEs will be coded using MedDRA version 23.0 or higher.

All reported AEs (whether treatment emergent or not) on both study URO-901-3005 and URO-901-3006 will be included in by-subject AE listings on the Safety Set Extension. Sorting will be by country, site, subject, date of event, SOC, PT and then verbatim description. An additional overall AE listing will be presented for subjects that were enrolled but not dosed with vibegron on URO-901-3006.

An AE will be considered treatment emergent (TEAE) if it begins or worsens in severity after the first dose of vibegron on study URO-901-3005 or URO-901-3006 through 5 days after the last dose of vibegron. Partial AE start dates will be imputed as detailed in [Section 4.2.3](#).

Summary tables will be based on TEAEs. The incidence of TEAEs will be presented using counts and percentages of subjects with TEAEs and tabulated by SOC and PT. SOC will be sorted in descending frequency and PT within SOC will be sorted by descending frequency based on the incidence across subjects overall. If a subject has multiple occurrences (start and stop) of an event associated with a specific SOC or PT within a SOC, a subject will only be counted once in the incidence count for the SOC or PT within SOC respectively.

An overall summary table of AEs will be presented detailing the number and percentage of subjects, and number of events for the following categories:

- At least one TEAE;

- At least one Treatment-Related TEAE;
- At least one Grade ≥ 3 TEAE (Mild = Grade 1, Moderate = Grade 2, Severe of Medically Significant = Grade 3, Life-Threatening = Grade 4, Death = Grade 5)
- At least one Grade ≥ 3 Treatment-Related TEAE;
- At least one Serious TEAE;
- At least one Serious Treatment-Related TEAE;
- At least one TEAE leading to Discontinuation from Study Medication;
- At least one TEAE of Special Interest;
- At least one Treatment-Related TEAE of Special Interest

Where not otherwise noted, all the following summaries are presented by PT:

- All TEAEs (by SOC and PT);
- Treatment-Related TEAEs (i.e., possibly or probably related);
- TEAEs occurring in 2% or more of the population;
- All TEAEs by SOC, PT, and maximum severity (where the maximum intensity per patient will be counted at each level of summarization);
- TEAEs with Grade ≥ 3 ;
- Treatment-Related TEAEs with Grade ≥ 3 ;
- Serious TEAEs;
- Treatment-Related Serious TEAEs;
- Fatal TEAEs;
- TEAEs leading to Discontinuation from Study Treatment;

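### SAP 5.4 and SAP Table 2 conflict on which pre-vibegron AEs are medical history; under 5.4, non-worsening ongoing AEs leave both summaries, and some men with hypertension can be flagged No for Pre-existing Hypertension

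*SAP*

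**What the plan says.** SAP Section 5.4 builds medical history from two sources. The first is the parent-study form: "Medical history will include all events entered on the medical history form in URO-901-3005". The second is AEs, specifically "any AEs with the end date prior to the first date of active treatment on either URO-901-3005 or URO-901-3006". The test for an AE is therefore its end date.

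SAP Table 2 (Section 4.2.4.1) has an AE category labelled "Prior (Summarized as Medical History". It takes AEs that start on or after parent-study consent and before the "date of first dose of vibegron in either study", and its end-date column imposes no limit. The test is therefore the start date.

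SAP Section 7.3 counts an AE as treatment emergent if "it begins or worsens in severity after the first dose of vibegron on study URO-901-3005 or URO-901-3006", up to 5 days after the last dose. Table 2 says the same in substance.

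SAP Section 5.2 makes medical history part of a stratifying variable: "Pre-existing hypertension will be defined as having a medical history of hypertension or Baseline hypertension". Baseline hypertension means systolic pressure of at least 140 mmHg or diastolic pressure of at least 90 mmHg. The flag splits a hypertension TEAE table (Section 7.3, Table 14.3.2.15) and the blood pressure and pulse change tables (Section 7.5).

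**The concern.** The two rules disagree about any AE that is already present and unresolved at the first vibegron dose. The 5.4 rule also gives an odd result: a hypertension AE that has resolved counts as history, while one the man still has does not, in a section whose title covers concomitant disease.

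The effect reaches beyond the history table because of the hypertension flag. Hypertension is an AE of special interest (Protocol Section 8.4.6), and safety is the primary objective. Consider a man who became hypertensive on placebo, started treatment, and reads below 140/90 before vibegron. The blood pressure exclusions in Protocol Section 5.2 do not keep him out. Under 5.4 he can be flagged No. If his hypertension later worsens, the TEAE is counted in the No stratum, where it reads like new hypertension on vibegron. He also sits in the No stratum of the blood pressure tables.

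**Working it through.** The plan states no figure on this point, so the check is to run each kind of AE through the rules. Let V be the first vibegron dose in either study.

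| Case | AE starts | State at V | Worsens after V | History under 5.4 | History under Table 2 | TEAE |
|---|---|---|---|---|---|---|
| 1 | before V | ended | n/a | yes | yes | no |
| 2 | before V | ongoing | no | **no** | yes | **no** |
| 3 | before V | ongoing | yes | no | yes | yes |
| 4 | on or after V | n/a | either | no | no | yes |

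Only case 2 falls outside both summaries, and only under 5.4. The table leaves aside one same-day exception: a Table 2 footnote drops from TEAEs an event starting on the day of V if its relatedness is marked not applicable.

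Next, the Pre-existing Hypertension flag. Take a man with a hypertension AE that started before V under one of the preferred terms in Section 5.2, and with no hypertension entry on the history form. Assume the search in 5.2 runs on medical history as defined by whichever rule is in force.

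| AE ongoing at V | Baseline BP ≥140 or ≥90 mmHg | Flag under 5.4 | Flag under Table 2 |
|---|---|---|---|
| no | no | Yes | Yes |
| no | yes | Yes | Yes |
| yes | no | **No** | Yes |
| yes | yes | Yes | Yes |

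One of the four combinations differs.

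The result also depends on which reading is the baseline, and the SAP gives two answers. Section 3.1.2: "Baseline will be established as the last observation prior to the first dose of vibegron". Section 4.3.4: "the last recorded value prior to first double-blind dose of study treatment will serve as the baseline measurement for safety endpoints". Under the first, the pressure criterion catches a switcher who is still at or above 140/90 just before vibegron, but misses one who is controlled. Under the second, the reading predates the placebo period and cannot detect hypertension that arose during it, so the third row becomes more likely.

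Size:

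- SAP Section 1.2.4 expects 100 one-year completers at about 33% dropout. The implied starting group is 100 / (1 − 0.33) = 149. Of about 300 men, 300 − 149 = 151, or about 150, would come from placebo. Check: 150 × 0.67 = 100.5, in line with the plan's 100.
- The share of switchers with a hypertension AE that began on placebo and is ongoing at V is not in the documents. Assumed range 1 to 5%: 0.01 × 150 = 1.5 and 0.05 × 150 = 7.5 men.
- These are ceilings for switchers under that assumption. Men with a history-form entry or a baseline reading at or above 140/90 are already Yes and should be subtracted.
- Men randomized to vibegron are exposed too, for AEs between parent-study consent and Day 1, over a shorter window. They are not in this count.

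**The case against.** The strongest reply is that Table 2 already places these AEs in medical history, so two passages disagree but no category of events is shown to be lost. That stands: the gap exists only if 5.4 is the rule programmed. It does not remove the need to choose, because one dataset cannot follow both and SAP Section 9 is silent.

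A reader might infer that every condition that began on placebo and continues escapes the TEAE tables. The documents do not support that, because worsening on vibegron makes it a TEAE under both Table 2 and Section 7.3. Nor do the events vanish. Section 7.3 lists all AEs from both studies whether treatment emergent or not, flags onset as before or on vibegron, and adds a hypertension history listing that takes in pre-treatment AEs with no end-date condition. The loss is from summary tables.

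A reader might also infer that Pre-existing Hypertension is misclassified generally. It is not: the pressure criterion and the history form each give Yes on their own, and only one combination changes.

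Finally, the study has no formal hypotheses and no inferential testing of safety data. Overall TEAE, serious AE and special-interest counts do not depend on 5.4. Table 14.3.2.16 is also unaffected, since it splits by Baseline Hypertension, which ignores medical history. All of this stands and limits the consequence.

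**Conclusion.** The conflict between Section 5.4 and Table 2 is real and unresolved. Section 5.4 is the outlier: Table 2, the onset flag and hypertension history listing in Section 7.3, and the definition of prior procedures in Section 5.5 all look at when something began or whether it preceded treatment, not at whether it had ended.

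The consequence is conditional. If 5.4 prevails, ongoing non-worsening AEs leave both summaries. A man can then be flagged No for Pre-existing Hypertension if four things hold together: a hypertension AE with a listed term that began before vibegron, still ongoing at the first dose, no history-form entry, and baseline pressure below 140/90.

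The number of such men cannot be derived from the documents. The ceiling of about 1.5 to 7.5 switchers rests on the inferred 150 and the assumed 1 to 5%; the upper end should not be read as an estimate. The outputs at risk are the history table, the Pre-existing Hypertension row at baseline, Table 14.3.2.15 and the blood pressure and pulse tables split by the flag. It is a consistency correction of modest reach, worth making because it touches an event of special interest in a safety study.

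**What to change.** In SAP Section 5.4, replace the end-date condition with the Table 2 rule: medical history includes all AEs with a start date before the first vibegron dose, whether or not they have ended. In Section 5.2, add that the search for a history of hypertension covers these AEs as well as the history form. An AE that starts before vibegron and later worsens would then be both history and a TEAE, which is consistent with both definitions; say so, to prevent queries.

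The split between Sections 3.1.2 and 4.3.4 on the safety baseline is a separate inconsistency. It should be settled at the same time, because it decides which blood pressure reading feeds the flag. A clause can also say where the same-day events excluded by the Table 2 footnote belong.

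The cost is one phrase in 5.4 and one sentence in 5.2, made before database lock, with a matching change to the derivation. No new data are needed.
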